The objective of this study is to determine how neurolens® influences contact lens discomfort in uncomfortable myopic soft contact lenses wearers. We hypothesize that uncomfortable soft contact lens wearers are experiencing some level of discomfort associated with increased vergence demand when looking at near targets and will experience discomfort relief when wearing neurolens® over their habitual soft contact lenses. Uncomfortable, myopic soft contact lens wearers will be recruited. Each participant will be masked and randomly assigned a placebo pair of spectacles or a neurolens® spectacle pair for approximately one month.

Study Design

A prospective, randomized clinical trial will be performed. Participants and investigators will be masked to the treatment.

Sample Size

This is the first study to explore the relationship between contact lens discomfort and neurolens® correction. The nature of this study is, therefore, exploratory and the data and results collected will be pilot in nature. A reasonable sample size goal has been determined to be 30-60 total participants (15-30 per treatment group).

PROTOCOL & CLINICAL TRIAL OUTLINE: Neurolens and Contact Lens Discomfort

NCT05801991

Principal Investigator: [name], OD, PhD

Document Date: 3/10/2025

Primary Outcome Variable

The primary outcome variable will be change in contact lens discomfort, as measured by the Contact Lens Dry Eye Questionnaire-8 (CLDEQ-8).^{9,10}

Secondary Outcome Variables:

Secondary outcome variables will be change in symptoms scores measured on the Convergence Insufficiency Treatment Trial (CISS), Headache Impact Test (HIT-6), and the Standard Patient Evaluation of Eye Dryness (SPEED).¹¹⁻¹³

Inclusion Criteria & Study Procedures:

Table 1 lists all study inclusion and exclusion criteria. Figure 1 outlines the general flow of the study design.

Study Materials

The neurolens® Measurement Device (nMD2; neurolens, Inc. Costa Mesa, CA) and the neurolens spectacle lenses are Class 1 Medical Devices (exempt).

The nMD2 is a desktop diagnostic instrument. The following is the description provided in the manufacturer's nMD2 Users Manual:

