Once all inclusion criteria have been confirmed, participants will be enrolled and assigned to a treatment group. Participants who do not meet all inclusion criteria will be excused from the study and compensated for their time (\$50). Participants who meet all inclusion criteria will be informed that they will receive their study compensation (\$100) upon completion of the study at the final visit.

Randomization to treatment group will be achieved using an online random number generator to determine the order of allocation (1:1) before subject enrollment. Participants will be enrolled and assigned to a treatment group in the order they qualify for enrollment at the baseline examination.

Enrolled participants will be provided with a \$100 credit card cash gift card to offset the cost of spectacle frames that can be purchased at the Ketchum Health University Eye Center Optical, or they can provide their own spectacle frame. Once a frame has been identified, it will be sent to the neurolens® lab for fabrication and placement of lenses depending on treatment group assignment. Participants in the placebo group will receive single vision plano lenses. Participants in the neurolens® group will receive lenses based on the measurements made by the neurolens® Measurement Device.

Participants will be contacted when their completed spectacles have arrived. At pick-up, each participant will be instructed to wear the spectacles full time over their habitual contact lenses. At this time, they will schedule the final study visit 35 ± 5 days after spectacle pick-up.

Final Examination

The final examination is anticipated to last approximately 30 minutes. At the final examination, participants will be instructed to return wearing their habitual soft contact lenses and the spectacles dispensed at the last visit. Visual acuity will be measured monocularly with the habitual soft contact lenses and study spectacles at distance (approximately 6 meters) with a high contrast Snellen chart. The spectacles will be removed and repeat measurements will be taken using the neurolens® Measurement Device. Participants will complete the CLDEQ-8, CISS, HIT-6 and SPEED surveys. Participants will be asked to report approximately how many hours per day and days per week they wore their contact lenses, and the same parameters for their time wearing the contact lenses with the study spectacles over the last 35 ± 5 days.

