After all measurements and surveys have been completed for all subjects, participants will be unmasked to the treatment group they are in. Both groups will be able to keep the spectacle lenses dispensed in the study, will be compensated for their time at both visits (\$100), and will be dismissed from the study.

PROTOCOL & CLINICAL TRIAL OUTLINE: Neurolens and Contact Lens Discomfort

NCT05801991

Principal Investigator: [name], OD, PhD

Document Date: 3/10/2025

[figure not shown]

Figure 1: Flow chart of study procedures

Informed Consent and Patient Privacy

Upon arriving at the baseline examination visit, all participants will sign an informed consent form. The form will explain the purpose of the study, any anticipated risks/benefits, and the rights the participant has. Each participant will be able to ask investigators questions and keep a copy of the informed consent form. As well, all participants will sign a Health Insurance Portability and Accountability Act (HIPAA) explaining that their health information is private and any personal health identifiers collected in the study will not be used in association with their identity and/or for any other purpose. Additionally, all participants will read and sign the MBKU COVID research consent document.

Statistical Analyses

Statistical analyses will be performed to compare the survey scores of the two treatment groups before and after treatment. ANOVA and/or Wilcoxon Rank testing will be used depending on the distribution of the data according to Shapiro statistics. Additional analyses will also be performed to determine if particular demographic information (gender, age, etc.) and/or clinical data (refractive error, wear time, etc.) influenced symptom changes as measured by the four surveys administered.

PROTOCOL & CLINICAL TRIAL OUTLINE: Neurolens and Contact Lens Discomfort

NCT05801991

Principal Investigator: [name], OD, PhD

Document Date: 3/10/2025

References:

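### The primary contrast is not defined and no estimate or interval is planned; the primary result should be the between-arm difference in CLDEQ-8 change with its 95% CI

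*Combined protocol and SAP*

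**What the plan says.** The Statistical Analyses section is one short paragraph. The comparison is given as "Statistical analyses will be performed to compare the survey scores of the two treatment groups before and after treatment". The method is given as "ANOVA and/or Wilcoxon Rank testing will be used depending on the distribution of the data according to Shapiro statistics". A last sentence adds exploratory analyses of demographic and clinical factors that may influence symptom change.

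The Primary Outcome Variable section names change in CLDEQ-8 but gives no contrast between arms and no summary measure. In Objective & Hypothesis, the expectation is that wearers "will experience discomfort relief when wearing neurolens" over their own contact lenses; that sentence does not mention placebo. The Sample Size section calls the study "exploratory and the data and results collected will be pilot in nature" and sets a goal of 30-60 participants, 15-30 per arm.

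Three other parts of the plan bear on the point. Table 1 requires a CLDEQ-8 of 17 or more, and the criteria are confirmed again at the baseline visit. The pre-screening score is not used as study data. Allocation is 1:1, and the placebo arm receives plano spectacles.

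**The concern.** The text leaves three things open.

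- **The contrast.** The ANOVA factors are not given. The Wilcoxon test could be the paired signed-rank test (within arm) or the two-sample rank-sum test (between arms). A before-after test in the neurolens arm alone would satisfy both the analysis sentence and the wording of the hypothesis.
- **The read-out.** Only tests are named. No section gives an effect estimate, an interval, a significance level or an important difference.
- **The use of the pilot.** The SD of change, which a follow-on trial would need for its sample size, is not listed as an output.

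Participants are selected on the same score that measures the outcome, and everyone receives a new pair of spectacles. Some fall in CLDEQ-8 is therefore expected in both arms whether or not the prism works. A before-after test counts that shared fall as relief; the between-arm difference cancels it. Separately, with 15-30 per arm a non-significant test is an ordinary result even when a moderate effect is real, so a bare p-value would not tell the reader what neurolens does.

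**Working it through.** **Inputs from the document:** 15-30 per arm; 1:1 allocation; entry at CLDEQ-8 of 17 or more at both pre-screening and baseline. **Not in the document, so assumed:** two-sided 5% level, no dropout, and all SDs, effects, population means and retest correlations. The sample size goal comes with no calculation, so there is no figure to reproduce.

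**1. Power of the between-arm t test on change.** The noncentrality is d × √(n/2), with 2n − 2 degrees of freedom.

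- n = 15, d = 0.5: 0.5 × √7.5 = 1.37; critical t (28 df) = 2.048; power 26%, so p>0.05 in 74%.
- n = 30, d = 0.5: 0.5 × √15 = 1.94; critical t (58 df) = 2.002; power 48%, so p>0.05 in 52%.
- d = 0.8: power 56% at 15 per arm and 86% at 30.
- Effect detectable with 80% power: 1.06 SD at 15 per arm and 0.74 SD at 30.

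**2. Precision of the between-arm difference.** The 95% half-width is t × SD × √(2/n).

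- n = 15: 2.048 × 0.365 = 0.75 SD.
- n = 30: 2.002 × 0.258 = 0.52 SD.
- If the SD of CLDEQ-8 change is 3-8 points (assumed), that is ±2.2 to ±6.0 points at 15 per arm and ±1.6 to ±4.1 points at 30.

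**3. Within-arm tests under regression to the mean only.** Model: score = true level + visit error, total SD 6, retest correlation ρ, no change in true level and no neurolens effect.

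If selection were on the baseline score alone, the expected fall would be (1 − ρ) × (mean of selected baselines − population mean).

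- Mean 16, ρ = 0.85: the threshold is (17 − 16)/6 = 0.167 SD above the mean. Selected participants average 0.907 × 6 = 5.44 points above it, so the fall is 0.15 × 5.44 = 0.8 points.
- Mean 10, ρ = 0.70: the threshold is (17 − 10)/6 = 1.167 SD above the mean. Selected participants average 1.660 × 6 = 9.96 points above it, so the fall is 0.30 × 9.96 = 3.0 points.

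Setting the pre-screening score aside weakens this effect but does not remove it. Simulating selection at 17 or more on both occasions gives falls of about 0.5 and 1.9 points at the same two corners. The results across mean 10-16 and ρ 0.70-0.85 are:

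| Result with no neurolens effect | 15 per arm | 30 per arm |
|---|---|---|
| Neurolens arm shows significant improvement (paired t) | about 8-35% | about 13-65% |
| Between-arm t test on change, two-sided | about 5% | about 5% |

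The nominal rate for the first row, in the direction of improvement, is 2.5%. The pattern of neurolens significant and placebo not occurs in about 8-25% of trials over the two sizes.

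**4. Sensitivity.**

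- With population mean 14-20, SD 5-7 and reliability 0.6-0.9, the fall is about 0.1-2.1 points. False relief occurs in 4-32% (15 per arm) and 5-58% (30 per arm).
- If both arms improve by 0.5 SD of change for any shared reason, the neurolens arm's before-after test is significant in 44% (15 per arm) and 76% (30 per arm). The between-arm test stays at about 5%.

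**The case against.** The strongest reply is that the sentence speaks of the two treatment groups. In a masked, randomised, placebo-controlled trial whose primary outcome is already change, the natural reading of that sentence with ANOVA is a between-arm comparison. A group-by-visit interaction would be exactly the contrast wanted here. This stands: a reader might infer that the plan commits to before-after tests, and the documents do not support that. They permit such tests without stating them, and the rates in step 3 apply only if that reading is adopted.

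A reader might also infer that a null result would be reported as no relief. The documents say nothing of the kind, and the pilot label argues against it. What remains is that no interval is planned to show which effects are still possible.

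Nor does this make 15-30 per arm the wrong size. That is acceptable for a declared pilot, and at 30 per arm a 0.8 SD effect would be found 86% of the time. The pilot label in fact favours estimation over testing.

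Last, all SDs, means and retest values are assumed. This also stands for the figures in points and the false-relief rates. Power and half-widths in SD units do not need those values.

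**Conclusion.** The point holds as a gap in definition, not as a planned error. The analysis text does not fix the primary contrast, and it promises no estimate or interval. If the open wording were settled as within-arm tests, false relief would occur in about 8-35% of trials at 15 per arm and 13-65% at 30, against about 5% for the two-sided between-arm test. These rates assume population mean 10-16, SD 6 and retest correlation 0.70-0.85, and fall to 4-5% at the mildest setting in the sensitivity range. If the wording were settled as a between-arm comparison of change, the false-relief problem would disappear. The missing interval would still matter, because a 0.5 SD effect gives p>0.05 in 74% to 52% of trials across the planned sizes. This is a worthwhile and cheap improvement; it does not invalidate the design.

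**What to change.** In Statistical Analyses, state that:

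- the primary result is the between-arm difference in mean CLDEQ-8 change, in points, with its two-sided 95% CI, preferably from a model adjusted for baseline CLDEQ-8;
- this replaces the Shapiro-driven choice between ANOVA and Wilcoxon as the primary analysis, and a two-sample rank-sum test on change is a sensitivity analysis only;
- CISS, HIT-6 and SPEED are reported in the same way;
- within-arm changes are descriptive;
- the observed SD of change is reported for sizing a follow-on trial.

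In Objective & Hypothesis, adding that relief is judged relative to the placebo spectacles would align the two sections.

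Cost: a few sentences, with no extra participants, visits or data. The one loss is the within-arm p-values.

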The nMD2 is a microprocessor-controlled system used to measure eye misalignment at distance and near. Eye misalignment is measured through a dissociative test where the eyes are shown independent non-fusible targets, and direction of gaze is measured. This measurement is combined with an associative test where peripheral fusion is attained, and central alignment is measured. Effectively this measurement of eye alignment is an objective measurement of the angle of strabismus, and/or an evaluation of binocular vision.

The nMD2 uses an eye tracking system along with a stereoscopic display to measure eye alignment at distance and at near. From this information, a nMD2 number is calculated which is to be used along with other clinical assessments in the diagnosis and management of visual disorders.

The neurolens spectacle lenses include a proprietary contour prism design that provides the patient with increasing prism from the distance to near portion of the lens. The prism value used in this study will be determined using the nMD2 device. No significant adverse events/risks are anticipated for any participant who is examined with the nMD2 device.

All other study materials and instrumentation are those that are used in a normal eye examination, including anterior segment slit lamp assessment with sodium fluorescein staining and Schirmer tear volume assessment. No significant adverse events/risks are anticipated for any participant who participates in the study and/or undergoes any study procedures.

PROTOCOL & CLINICAL TRIAL OUTLINE: Neurolens and Contact Lens Discomfort

NCT05801991

Principal Investigator: [name], OD, PhD

Document Date: 3/10/2025

Table 1: Inclusion/Exclusion criteria

- Uncomfortable soft contact lens wearers (CLDEQ-8 \geq 17 points)¹⁰
- Adult, pre-presbyopic age range (18 – 35 years)
- Visual acuity of 20/25 or better in each eye with habitual contact lenses
- Soft, spherical, single vision soft contact lens wearer:
 - *Habitual contact lens sphere power -0.75 D or more myopic
 - *Habitual contact lens are spherical design
 - *Habitual soft contact lenses are single vision design
 - *Valid contact lens prescription at the date of the baseline
- No significant subjective over-refraction in either eye with habitual soft contact lenses
 - *Sphere: \leq 0.50 D myopia, \leq 0.50 D hyperopia
 - *Cylinder: \leq 0.75 D
- No history of ocular surgery
- No history of ocular disease, amblyopia, strabismus, or vision therapy

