If potential participants utilize the QR code included on the advertisement, the QR code will lead them to an online version of the CLDEQ-8 that the potential participant will complete. If their score qualifies them for the study, they will be instructed to contact study coordinators via phone or email. The study coordinators will then complete screening as described above.

The score obtained on the pre-screening CLDEQ-8 will not be used in the study.

Baseline Examination, Participant Enrollment, & Randomization

The baseline and enrollment examination is expected to last approximately one hour. At the baseline examination, all inclusion criteria will be confirmed again. Informed consent and HIPAA forms will be distributed to and signed by each participant. Participants will be asked to bring a copy of their current contact lens prescription and/or the boxes/blister packages of their current contact lenses to confirm prescription information.

Visual acuity will be measured monocularly with the habitual soft contact lenses at distance (approximately 6 meters) with a high contrast Snellen chart. Subjective over-refraction will be performed using a phoropter. These measurements will not influence eligibility for study inclusion. The CLDEQ-8, CISS, HIT-6, and SPEED questionnaires will be administered on an iPad.

The fit of the habitual soft contact lenses will be assessed with a slit lamp. The lenses will be removed and the patients will wait approximately ten minutes to allow the tear film to equilibrate. The neurolens® Measurement Device will then be used to obtain objective binocular vision measurements while the contact lenses have been removed, the tear film has equilibrated, and before topical fluorescein has been instilled. Topical fluorescein will be instilled to measure ocular surface staining and tear break-up time. General corneal, conjunctival, and anterior segment health will be assessed in the slit lamp. Schirmer

PROTOCOL & CLINICAL TRIAL OUTLINE: Neurolens and Contact Lens Discomfort

NCT05801991

Principal Investigator: [name], OD, PhD

Document Date: 3/10/2025

strips will be instilled in the lower temporal canthus of the right eye for five minutes to determine Schirmer score.

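### A Shapiro pre-test on unspecified data chooses between ANOVA and/or Wilcoxon, so change in CLDEQ-8 has no single fixed primary test

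*Combined protocol and SAP*

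**What the plan says.** The Primary Outcome Variable section states: "The primary outcome variable will be change in contact lens discomfort", measured by the CLDEQ-8. Change in CISS, HIT-6 and SPEED is secondary.

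The Statistical Analyses section is the only analysis text. It says "Statistical analyses will be performed to compare the survey scores of the two treatment groups before and after treatment", and then "ANOVA and/or Wilcoxon Rank testing will be used depending on the distribution of the data according to Shapiro statistics". A last sentence adds exploratory analyses of demographic and clinical factors.

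Table 1 admits "Uncomfortable soft contact lens wearers" with a CLDEQ-8 of at least 17. The Baseline Examination section adds: "At the baseline examination, all inclusion criteria will be confirmed again". The pre-screening score is not used, so the analysed baseline score is one that has itself had to reach 17.

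The Sample Size section aims for 30–60 participants (15–30 per arm) and calls the study exploratory and pilot. No significance level is given.

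**The concern.** Five things about the primary test are left open:

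- which variable goes into Shapiro (baseline, final, change or model residuals);
- whether it is pooled or per arm, and at what threshold;
- which ANOVA is meant;
- whether Wilcoxon means the rank-sum test (between arms) or the signed-rank test (within an arm);
- which result is the primary one if both tests are run, as the and/or wording permits.

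The test behind the trial's one primary p-value is thus settled only after the data are in hand, and two p-values could stand side by side.

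The entry rule adds a problem specific to this trial. Cutting CLDEQ-8 off at 17 skews the baseline distribution. If Shapiro is run on those raw scores, it can send the primary comparison to a rank test although change gives no reason for it.

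**Working it through.** **The plan's own figures.** None can be reproduced on this point: no alpha, SD, effect or Shapiro threshold is stated. The check is a simulation.

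**Inputs from the documents.** Cut-off 17, applied at pre-screening and again at baseline; 15 or 30 per arm; 1:1 allocation; outcome is change in CLDEQ-8.

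**Assumed inputs.** CLDEQ-8 maximum 37; whole-point scores; normal true scores and errors; 5% for Shapiro and for the main test, two-sided; population mean *m*, SD *s* and reliability *ρ* as tabulated.

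**Model.** Observed score = *T* + *e*, with Var(*T*) = *ρs*² and Var(*e*) = (1 − *ρ*)*s*². Pre-screen, baseline and final scores share *T* and have independent errors. A person enters if the pre-screen and baseline scores are both at least 17. Change = final − baseline. There were 2,000 trials per row, so the 95% simulation error is about 1 point near 5% (1.96 × √(0.05 × 0.95/2000) = 0.0096) and about 2 points for mid-range percentages.

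**Step 1: no treatment effect.** Entries are percentages of trials. The first two results columns are Shapiro rejections, of pooled baseline scores and of change (residuals within arm). The rest are false-positive rates.

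| *m*, *s*, *ρ* | n/arm | Shapiro, baseline | Shapiro, change | t-test on change | Wilcoxon on change | Gated on change | Gated on baseline | Smaller p | ANCOVA |
|---|---|---|---|---|---|---|---|---|---|
| 12, 7, 0.6 | 15 | 78.0 | 4.8 | 5.0 | 4.3 | 5.1 | 4.6 | 5.4 | 4.4 |
| 12, 7, 0.6 | 30 | 99.5 | 5.1 | 5.7 | 4.9 | 5.7 | 5.0 | 6.3 | 5.4 |
| 15, 6, 0.7 | 15 | 67.8 | 5.1 | 4.8 | 4.0 | 5.0 | 4.4 | 5.3 | 5.2 |
| 15, 6, 0.7 | 30 | 98.6 | 6.0 | 5.6 | 5.3 | 5.7 | 5.3 | 6.4 | 5.1 |
| 15, 6, 0.5 | 15 | 74.4 | 5.8 | 5.5 | 4.8 | 5.6 | 5.0 | 5.9 | 5.2 |
| 15, 6, 0.5 | 30 | 99.4 | 5.9 | 5.4 | 4.9 | 5.6 | 4.9 | 6.1 | 5.3 |
| 20, 6, 0.7 | 15 | 38.9 | 5.6 | 5.1 | 4.7 | 5.2 | 5.0 | 5.5 | 5.0 |
| 20, 6, 0.7 | 30 | 80.9 | 5.3 | 4.9 | 4.8 | 4.9 | 4.7 | 5.8 | 4.4 |

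The baseline score does not depend on the treatment effect. A second run of the lowest row gave 36.3%, and the two average (38.9 + 36.3)/2 = 37.6%. A further set of runs, again with assumed means, SDs and reliabilities, gave 37–83% at 30 participants, 81–99.8% at 60, and 4–8% for change.

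**Step 2: cost in type I error.** A test gated by Shapiro has a false-positive rate of 4.4–5.7% in the table (about 4–6% in the further runs). Always taking the smaller p gives 5.3–6.4% (4.5–7% in the further runs). Compared with the t-test row by row, the excess runs from 5.4 − 5.0 = 0.4 to 5.8 − 4.9 = 0.9 points.

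**Step 3: how often the choice changes the result.** With an assumed 3-point difference, one of the t-test and Wilcoxon is significant and the other is not in 5.9–7.6% of trials (4–8% in the further runs). With no effect the figure is 1.1–2.1%.

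**Step 4: what one fixed analysis gives.** Power (%) for the same 3-point difference, rows in the order above:

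- ANCOVA: 31.8, 54.4, 44.8, 78.2, 32.3, 61.1, 45.2, 78.0
- t-test on change: 29.3, 50.0, 41.8, 74.5, 30.2, 55.6, 40.6, 72.3
- Wilcoxon on change: 26.6, 47.7, 39.5, 71.8, 27.4, 53.7, 38.6, 70.7

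ANCOVA gains 2.1 (32.3 − 30.2) to 5.7 (78.0 − 72.3) points over the t-test, and 4.9 (32.3 − 27.4) to 7.4 (61.1 − 53.7) points over Wilcoxon. Its type I error is 4.4–5.4%.

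**The case against.** The strongest reply is that the plan never says Shapiro is run on baseline scores. The primary outcome is change, so a careful analyst would test change or residuals, and there the cut-off hardly matters. This stands: the truncation argument is conditional on a reading that the text permits but does not state.

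A reader might infer that the cut-off makes baseline scores fail Shapiro almost automatically. That goes too far. It is near certain only at about 60 pooled participants with a population mean near or below 17. With baseline truncation alone and an assumed mean of 24 and SD of 5, rejection is 7%, 12% and 29% at 15, 30 and 60 scores. The documents give no mean or SD that would settle the matter.

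A reader might also infer serious inflation of the error rate. The Shapiro rule does not produce it. Rates of 9–12% arise only if the choice between final score and change is left open as well. That is a separate freedom, and the primary outcome definition answers it by naming change.

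Nor does a rank test leave the trial without an effect in CLDEQ-8 points: a Hodges–Lehmann shift with a confidence interval, or mean change per arm, can accompany it.

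The masking text does not show that the choice would be made with allocation known. "After all measurements and surveys have been completed for all subjects, participants will be unmasked" concerns participants. Study Design masks investigators, and a pooled Shapiro test needs no group labels.

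Finally, this is a declared pilot. That lowers the stakes, but the trial is randomised and masked and names one primary outcome, so naming one analysis for it is still reasonable.

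**Conclusion.** The gap is real. No single test, tested variable, threshold or contrast is fixed for the primary outcome, and nothing says which of two permitted results counts. This is more than missing detail, because the rule that is stated makes the primary test depend on the data.

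Its consequence is modest. False-positive rates stay near 5%, at most about 7% under the least favourable choice. What remains is analytic freedom, which decides significance in about 4–8% of trials with an assumed 3-point effect. The wrong-trigger problem, at roughly 37–83% of trials with 30 participants and 81–100% with 60, applies only if raw baseline scores are tested.

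All these figures rest on assumed means, SDs, reliabilities, normal errors and a 5% level. Skewed errors or floor effects would raise the Shapiro rejection rate for change. This is a cheap improvement, not a reason to doubt the design.

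**What to change.** Replace the test-selection sentence with:

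> For each survey, the between-arm difference in change (final minus baseline) is estimated and tested once with a linear model adjusted for the baseline score (ANCOVA), two-sided 5%, with no normality pre-test, and reported in scale points with a 95% confidence interval. A Wilcoxon rank-sum test on the same change is a labelled sensitivity analysis.

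Name CLDEQ-8 as the primary result, and date the text before anyone analysing the data sees the allocation. ANCOVA conditions on baseline, so the truncated shape of the baseline score gives no reason for a pre-test.

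Cost: one sentence, with no new data or visits. The sponsor gives up the option of leading with the rank test.
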